##### Exclusion criteria:

- Known *BRCA* mutation with no diagnosis of invasive breast cancer;
- Diagnosis of ovarian cancer or other malignancies with no history of invasive breast cancer;
- Diagnosis of hereditary or familial invasive breast cancer without *BRCA* mutation or with *BRCA* genes not tested;
- Diagnosis of invasive breast cancer with germline *BRCA* variants of unknown significance.

### 3.2. Contact with Investigators

The study chairs and secretariat of this project will invite investigators from different institutions worldwide to participate in this project.

Upon agreement, investigators will be requested to provide anonymous individual patient data. A principal contact will be requested per Institution in case of data clarification needs. A timeframe of 4 months is given for data collection from each Institution after a positive opinion is granted by the respective Independent Ethical Committee / Institutional Review Board.

### 3.3. Data collection

For all consecutive eligible patients included in the study from each participating Institution, their medical records will be retrieved and anonymized data entered into a database. The following information will be collected, if available:

- 1) Baseline characteristics: body mass index; smoking habit; age at menarche; age at menopause; menopausal status at the time of breast cancer diagnosis; use of birth control pills; prior children before breast cancer diagnosis; history of spontaneous abortion; history of induced abortion; prior treatment for infertility; prior gynecological surgery and/or medical history with possible impact on fertility.
- 2) Breast cancer history: date of diagnosis; age at diagnosis; disease stage; laterality of the primary tumor; type of breast and axillary surgery; use of breast reconstruction surgery; grade; histology; tumor size and nodal status (for patients who underwent primary systemic therapy, only clinical tumor size and nodal status will be collected); hormone receptor status (estrogen and progesterone receptors); HER2 status.
- 3) Treatment of the primary tumor: timing of systemic therapy administration; use of chemotherapy (type and number of cycles); use of endocrine therapy (type and duration); use of anti-HER2 targeted therapy (type and duration); use of radiotherapy.
- 4) Survival status: any recurrence of invasive breast cancer including date of the event; any second primary breast cancer including date of the event; any second primary malignancy including date of the event; date of last follow-up and/or death; cause of death (breast cancer-related or not).
- 5) Ovarian function after chemotherapy: treatment-induced POF; age at menopause.

6) Pregnancy after breast cancer: any pregnancy including date of the event; pregnancy outcome; gestational age at delivery; any pregnancy/fetal/birth complications; breastfeeding and its duration; use and type of ART.

7) BRCA mutation: date of *BRCA* testing; type of *BRCA* mutation; use and date of breast prophylactic surgery; use and date of gynecological prophylactic surgery.

8) Additional information: diagnosis of breast cancer during pregnancy, availability of digital scanned images for TILs analysis

Data can be sent in confidence to [name] ([[contact]](mailto:[contact])) and [name] ([[contact]](mailto:[contact])) where they will be held secure and only used for the purposes of this study. Analyses will only be undertaken under the supervision of the study statisticians.

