Concerns about fertility preservation and future chance of achieving a pregnancy are prevalent issues affecting young breast cancer patients [8]. Hence, accordingly, major international guidelines recommend physicians to address with patients as part of informed consent before anticancer therapies the possibility of developing POF and infertility, and then to discuss fertility preservation options in interested patients [9–11]. Specific issues on this regard should be considered in patients with *BRCA* mutation in the context of their unique concerns [12]. For carriers, given the increasing risk of ovarian cancer with age, bilateral salpingo-oophorectomy is generally recommended for both *BRCA1* and *BRCA2* carriers between the ages of 35 and 40 years and upon completion of childbearing [13]. Moreover, some carriers wish to eliminate the mutation from future offspring through pre-implantation genetic diagnosis [14]. Finally, given the increasing risk of ovarian and breast cancer and the risk of developing long-term treatment-related POF [15], the window for fertility and pregnancy may be narrow in such young women. Of note, although, the last years have brought many safety and efficacy data on the available options for fertility preservation increasing the chances of

future offspring in cancer survivors, numerous challenges remain for young breast cancer patients considering fertility preservation and to have a pregnancy after the end of treatments, especially for those with *BRCA* mutations. Thus, further research is needed in the field; particularly, reproduction studies to address the specific issues of women with *BRCA* mutations are lacking and should be considered a research priority.

Approximately 40% to 50% of women in whom breast cancer is diagnosed during childbearing age wish to have a subsequent pregnancy [16]. However, the percentage of breast cancer patients reported in the literature that has at least one full-term pregnancy after breast cancer diagnosis is very low. Of note, among cancer survivors, breast cancer patients have the lowest pregnancy rate with an overall 67% reduction in the chance of giving birth after cancer treatment as compared to the general population [17]. This observation reflects not only the damage to ovarian reserve due to the gonadotoxic treatments required, but also patient and provider concerns related to a possible negative impact of pregnancy on the evolution of breast cancer [18].

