##### Inclusion criteria:

- Diagnosis of invasive breast cancer between January 2000 and December 2020;
- Breast cancer diagnosis at the age of  $\leq 40$  years;
- Known presence of germline *BRCA* pathogenic variant.

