pregnant cohort will be compared to those of patients in the non-pregnant cohort. To reduce the impact of selection bias (i.e. guaranteed time bias), two analyses will be performed. In the extended Cox model analysis with occurrence of pregnancy as a time-varying covariate, all eligible patients included in the study will be considered. In the “case-control” analysis, each patient in the pregnant cohort (case) will be matched with 3 patients from the non-pregnant cohort (controls). To adjust for guaranteed time bias, each patient in the non-pregnant cohort should have a disease-free interval equal to or longer than the time elapsing between breast cancer diagnosis and date of pregnancy of the matched patient in the pregnant cohort. Patients who became pregnant after the date of the DFS event will be dropped from this analysis. Patients will be also matched according to several variables including type of *BRCA* mutation (*BRCA1* vs. *BRCA2*), hormone receptor status (positive vs. negative), nodal status (negative vs. positive), and year at diagnosis ( $\pm 2.5$  years). Because all included patients are aged  $\leq 40$  years at the time of diagnosis, matching according to age will not be performed. The matching will be done centrally at the coordinating center. Two data sets will be constituted: one for the cases and one for the potential controls. Cases will be sorted randomly and matching will be done starting for the first case until the last one. For each case, all possible controls will be extracted from the data set of potential controls. If they are only 2 controls available, matching criteria will be relaxed one by one (starting from year of diagnosis, etc) until at least a third control is found. It is anticipated, given the expected low rate of cases in the full database, to reach matching for almost each case. In these analyses, all survival endpoints will be calculated from the date of pregnancy until the date of the event. In the non-pregnant cohort, survival endpoints will be calculated from the date of diagnosis, adding the time elapsing between diagnosis and pregnancy of the matched pregnant case.

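### The BRCA test date is collected but never used, so survival time guaranteed by testing stays in the risk sets; the risk-reducing-surgery analysis is most exposed

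*Combined protocol and SAP*

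**What the plan says.** - **Entry.** The inclusion criteria (Section 3.1) require "Known presence of germline *BRCA* pathogenic variant". The exclusion criteria remove women "without *BRCA* mutation or with *BRCA* genes not tested". Diagnoses run from January 2000 to December 2020, and no maximum interval from diagnosis to test is given.
- **Data.** Section 3.3 lists "date of *BRCA* testing" and "use and date of breast prophylactic surgery; use and date of gynecological prophylactic surgery", all to be collected if available.
- **Guaranteed time.** Section 4 has two measures. The first is a Cox model: "In the extended Cox model analysis with occurrence of pregnancy as a time-varying covariate, all eligible patients included in the study will be considered". Its time origin is not stated; diagnosis is implied. The second is the matched analysis, in which each control must have been disease-free for at least the case's interval to pregnancy. There, for cases, "all survival endpoints will be calculated from the date of pregnancy until the date of the event", and for controls "survival endpoints will be calculated from the date of diagnosis, adding the time elapsing between diagnosis and pregnancy of the matched pregnant case".
- **Surgery.** Amendment 1 added the prognostic impact of risk-reducing surgery as a secondary objective. Section 4 gives no method specific to it. It does not say that surgery is time-varying, and it states no time origin.
- **Test date.** Section 4 has no delayed entry, no restriction to women tested near diagnosis, and no sensitivity analysis on test timing.

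**The concern.** Eligibility imposes a second survival condition besides survival to pregnancy. A woman who died untested cannot be in the data, and a woman tested some years after diagnosis was certain to be alive until then. If her pre-test time counts as time at risk, it adds person-time in which no death could be recorded (left truncation).

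The plan accepts that guaranteed time must be handled, but handles only the part before pregnancy. The matched analysis does not start at diagnosis, yet it is not immune: a woman tested after her index date could not have died between that date and her test.

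Two results are directly at stake. Absolute OS can look too good. The surgery hazard ratio can be distorted even with correctly dated exposure, because the death-free time falls almost wholly in the unoperated person-time.

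**Working it through.** The documents give no distribution of test delay, no OS rate and no figure on this point, so there is nothing of the plan's own to reproduce. The power statement (0.83 and 0.62) does not depend on it. What follows illustrates size on assumed inputs.

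**Assumptions.** Share p of women tested late: 30% to 70%. Mean delay among them: 3 to 5 years, exponential. The rest are tested at diagnosis. Deaths are exponential, with true 10-year OS of 0.90, 0.80 or 0.70. Test timing is unrelated to prognosis unless stated.

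**Step 1. Absolute OS, by formula.** Let λ be the death rate and μ = 1/(mean delay).

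- Share of women who can enter: (1 − p) + p·μ/(μ + λ).
- Share who can enter and are alive at t: exp(−λt) − p·[λ/(λ + μ)]·exp(−(λ + μ)t).
- OS counted from diagnosis is the second divided by the first.

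Take true 10-year OS 0.80, p = 0.5, mean delay 3 years:

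- λ = −ln(0.80)/10 = 0.0223; μ = 0.3333; μ/(μ + λ) = 0.937.
- Can enter: 0.5 + 0.5 × 0.937 = 0.969.
- Can enter and alive at 10 years: 0.80 − 0.5 × 0.0627 × exp(−3.556) = 0.799.
- Apparent OS: 0.799/0.969 = 0.825, against a true 0.80.

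**Step 2. Absolute OS, by simulation.** This also requires women to be under follow-up at the test, which makes the excess slightly smaller.

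| True 10-year OS | Counted from diagnosis | Entry at test date |
|---|---|---|
| 0.90 | 0.907–0.923 | 0.90 |
| 0.80 | 0.813–0.844 | 0.80 |
| 0.70 | 0.718–0.761 | 0.70 |

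The excess runs from 0.7 points (0.907 − 0.90) to 6.1 points (0.761 − 0.70).

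**Step 3. Surgery and OS, true hazard ratio 1.** Surgery is possible only after the test (60% operated, on average 1.5 years later). Follow-up limits are uniform between 2 and 22 years. The hazard ratio is a Mantel-Haenszel rate ratio stratified on time since diagnosis, which is close to Cox.

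| Late share, mean delay | Time-varying surgery, from diagnosis | Time-varying surgery, entry at test |
|---|---|---|
| 30%, 3 years | 1.08–1.09 | 0.99–1.00 |
| 50%, 3 years | 1.15–1.16 | 1.00 |
| 50%, 5 years | 1.24–1.25 | 0.99–1.01 |
| 70%, 5 years | 1.32–1.33 | 1.00–1.01 |

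Ranges are over the three OS levels. With surgery coded ever/never (true 10-year OS 0.80), the null hazard ratio is about 0.74 from diagnosis and 0.72–0.73 with entry at the test. Delayed entry alone therefore does not repair that coding.

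**Step 4. Pregnancy and OS, true hazard ratio 1, counted from diagnosis.**

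- Test timing unrelated to pregnancy: 0.98–1.02, the same with either entry rule up to simulation error.
- Pregnancy only after testing: 1.03–1.09.
- Late-tested women conceive twice as often: 0.97–0.98.
- Pregnancy 50–75% less likely after testing: 0.93–0.98.

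Entry at the test date returns 1.00 in the second and third cases and 0.99–1.02 in the fourth.

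**Step 5. Recurrence as the reason for testing.** Assume recurrence at 6% a year, death after recurrence at 25% a year, 50% tested late (mean 4 years), and true 10-year OS 0.695. The percentage is the share of late-tested women relapsing before their test whose test is prompted by the relapse.

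| Tests prompted by recurrence | OS from diagnosis | OS with delayed entry |
|---|---|---|
| none | 0.721 | 0.696 |
| 60% | 0.704 | 0.677 |
| 90% | 0.696 | 0.667 |

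With heavy prompting, 5-year DFS counted from diagnosis was 0.739 against a true 0.741, and as low as 0.718 when other testing was rarer. In a separate run with prompting (30–50% tested late, mean 3–4 years), the null time-varying surgery hazard ratio was about 1.06–1.16 from diagnosis and 0.97–1.01 with entry at the test.

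**The case against.** The strongest objection is that delayed entry can be worse than the problem. It assumes that test timing is unrelated to prognosis. If recurrence prompts testing, women enter the OS risk set at high hazard, and Step 5 shows absolute OS then pushed below the truth while the count from diagnosis comes closer to it. The documents do not say why women were tested. This stands: delayed entry should not replace the main OS or BCSS analysis. It does not defeat the surgery point, where delayed entry stayed near 1.0 even with prompting.

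A second objection is that the pregnancy comparison need not be affected. This also stands. A reader might infer a bias in favour of pregnancy from the Background, where "bilateral salpingo-oophorectomy is generally recommended for both" BRCA1 and BRCA2 carriers. But that sentence ties the surgery to an age range and to completed childbearing, and the same section says that some carriers seek pre-implantation genetic diagnosis, which implies pregnancy after testing. These point in opposite directions, as do the results in Step 4.

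Third, a reader might take all follow-up to start at diagnosis. The matched analysis does not, and for the all-patient Cox model diagnosis is implied rather than stated.

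Finally, surgery is a secondary objective and its bias depends first on how surgery is coded, which the plan leaves open. That is fair, and the coding has to be fixed together with the entry time.

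**Conclusion.** The gap is real: entry is conditional on a test that may come long after diagnosis, its date is collected, and no analysis accounts for survival up to it. It merits a change to the plan.

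- **Surgery objective:** clearest effect. A null time-varying OS hazard ratio reads about 1.1 to 1.3 from diagnosis (about 1.06 to 1.16 in the run where recurrence prompts testing) and about 1.0 with entry at the test.
- **Absolute OS:** overstated by about 1 to 6 points if testing is not prompted by recurrence; less, or hardly at all, if it is.
- **Pregnancy and OS:** biased only if test timing is associated with pregnancy. The direction cannot be derived from the documents.
- **DFS:** a reader might infer that it is inflated too. That is not supported, because a woman first tested after recurrence enters together with her event; the bias can go either way.

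Every size rests on assumed delay distributions and death rates. The direction for surgery also assumes that surgery follows the test and is coded as time-varying.

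**What to change.** 1. **Risk-reducing-surgery models:** code surgery as time-varying and enter each woman at the later of diagnosis and BRCA test date. State the time origin.
2. **OS and BCSS by pregnancy, and absolute survival:** keep the planned analyses and prespecify two sensitivity analyses. One uses delayed entry at the test date; in the matched set, entry is at the later of index and test date, with controls already tested. The other is restricted to women tested near diagnosis and before any recurrence, because delayed entry alone is biased if recurrence prompts testing.
3. **DFS:** add the same as sensitivity analyses, leaving out women tested after their DFS event.
4. **Missing test dates:** state a rule, since dates are collected only if available, and report how many are missing.

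**Cost.** No new data field is needed, only an entry-time variable and time-dependent coding of surgery. Events before testing and women without a test date drop out, so intervals widen slightly. In one assumed scenario with 40% tested late, about 8–10% of DFS events were lost. Tabulating the interval from diagnosis to test would show how much of this matters in the actual data.

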## 4. STATISTICS

The achievement of pregnancy after diagnosis of breast cancer will be the criteria used to distinguish between two cohorts of patients: women with no subsequent pregnancies after breast cancer diagnosis (“non-pregnant cohort”), and women with one or more pregnancies any time after breast cancer diagnosis (“pregnant cohort”). Pregnancies could have resulted in live births, therapeutic or spontaneous abortions.

More than 2000 non-pregnant *BRCA* mutated breast cancer patients and more than 200 pregnant *BRCA* mutated breast cancer patients are expected to be included in the present study (estimated numbers, considering an incidence of pregnancy of approximately 10%).

To evaluate the prognostic impact of pregnancy following breast cancer diagnosis in *BRCA* mutated survivors, three survival endpoints will be considered in the two cohorts: DFS (as primary endpoint) BCSS (as secondary endpoint) and OS (as secondary endpoint). DFS event is defined by the occurrence of one of the following invasive events: local recurrence, distant metastases, contralateral or ipsilateral breast tumor, second primary malignancy, or death from any cause. BCSS event is defined as death from breast cancer. OS event is defined as death from any cause. For DFS, observation times of patients without the event will be censored on the date of their last contact. Using individual patient data from all patients included in the study, survival outcomes of patients in the

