The prognostic impact (in terms of DFS, BCSS and OS) of pregnancy following breast cancer diagnosis will be then evaluated in various subgroups of *BRCA* mutated survivors according to: type of *BRCA* mutation (*BRCA1* vs. *BRCA2*), hormone receptor status (positive vs. negative), HER2 status (positive vs. negative), exposure to chemotherapy (prior exposure vs. no prior exposure), exposure to endocrine therapy (prior exposure vs. no prior exposure), interval between diagnosis and pregnancy ( $\leq 2$  years vs.  $> 2$  years after diagnosis), outcome of pregnancy (abortion vs. completed pregnancy), and breastfeeding status (breastfeeding vs. no breastfeeding).

Considering a rate of pregnancy of approximately 10%, with 2000 non-pregnant and 200 pregnant *BRCA* mutated breast cancer patients, assuming a DFS rate of 65% at 5 years in the non-pregnant cohort [21], the study will have a power of 0.83 to detect a hazard ratio of 0.75 and a power of 0.62

to detect a hazard ratio of 0.80 in favor of the pregnant cohort, at a two-sided significance level 0.05 (accrual duration 2000-2020, total study duration 2000-2030).

The rate of pregnancy following breast cancer diagnosis will be computed according to the Kaplan-Meier method. A possible increasing or decreasing trend in rate of pregnancy following breast cancer over the years will be also assessed.

The statistical analysis to evaluate the pregnancy, fetal and obstetrical outcomes of the pregnancies following breast cancer diagnosis in *BRCA* mutated survivors will be mainly descriptive and will include the following parameters:

1. Gestational age at delivery;
2. Incidence of early pre-term (< 34 weeks), late-preterm (34-36 weeks) and full-term ( $\geq$  37 weeks) pregnancies;
3. Number of pregnancies resulting in live birth and number of children born;
4. Incidence of induced and spontaneous abortion;
5. Incidence and nature of pregnancy complications (if any);
6. Incidence and nature of fetal complication and/or congenital malformations (if any);
7. Incidence and nature of obstetrical complications (if any).

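### Women who have already had risk-reducing oophorectomy can serve as comparators for pregnant women, which may bias the DFS hazard ratio against pregnancy

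*Combined protocol and SAP*

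**What the plan says.** Section 4 (Statistics) compares pregnant and non-pregnant women in two ways.

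- **Matched analysis.** Each case gets three controls. A control must have been disease-free for at least the case's time from diagnosis to pregnancy, and her follow-up starts at that same elapsed time. The section continues: "Patients will be also matched according to several variables including type of" BRCA mutation, and then names hormone receptor status, nodal status and year of diagnosis. Age is deliberately not matched. The Synopsis gives the same factors.
- **Extended Cox model.** All eligible women enter. Pregnancy is the only time-varying covariate named.

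Neither analysis has a condition on risk-reducing surgery or on ability to conceive. Multivariate Cox models are mentioned at the end of Section 4 without a covariate list.

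On the endpoint, the section states: "DFS event is defined by the occurrence of one of the following invasive events". The list that follows includes new breast tumours on either side and second primary malignancies.

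Section 1 says "bilateral salpingo-oophorectomy is generally recommended for both" BRCA1 and BRCA2 carriers, and ties the timing to age 35 to 40 and to having finished childbearing.

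Section 3.3 requests the "use and date of gynecological prophylactic surgery" and the same for breast surgery, where records hold them. Sections 2 and 4 use these data only to describe care and in a separate secondary analysis of prognosis.

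**The concern.** By the plan's own background, oophorectomy goes with not intending a further pregnancy. A woman operated on early almost leaves the group that could become a case, yet remains available as a control and keeps adding non-pregnant time to the Cox model. Leaving age unmatched can add to this, because a control near 40 may be paired with a younger case.

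If the operation lowers the rate of second primaries, part of the comparator group is protected on the primary endpoint for a reason unrelated to pregnancy. Surgery after childbearing may follow from the pregnancy, so adjusting for it is debatable. Surgery before the index date cannot follow from that pregnancy; it is a baseline imbalance of the kind matching is meant to remove.

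The study asks whether pregnancy is safe. A tilt in this direction could suggest harm where there is none, or hide a benefit of the size the study is powered to find.

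**Working it through.** **1. The plan's power figure.** Inputs from Section 4: "Considering a rate of pregnancy of approximately 10%, with 2000 non-pregnant and 200 pregnant" patients; "assuming a DFS rate of 65% at 5 years in the non-pregnant cohort"; two-sided 0.05.

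- Hazard = -ln(0.65)/5 = 0.0862 per year.
- With 10 years of follow-up for everyone, events at HR 0.75 = 2000 × (1 - e^(-0.862)) + 200 × (1 - e^(-0.646)) = 1155 + 95 = 1250.
- Schoenfeld power = Φ(√(1250 × 1/11 × 10/11) × |ln 0.75| - 1.96) = Φ(0.96) = 0.83.
- At HR 0.80, with 1255 events, power is 0.62.

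Both agree with the stated figures. (Uniform accrual over 2000-2020 with follow-up to 2030 gives 0.93 and 0.76 instead, so the basis of the printed power deserves a line of clarification. It does not affect this point.)

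**2. Bias from an imbalance in surgery.** Let p0 and p1 be the shares of controls and cases operated on, and h the DFS hazard ratio for surgery. Under approximate proportional hazards,

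B = (1 - p1 + p1·h) / (1 - p0 + p0·h), and apparent HR = true HR × B.

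The documents give none of p0, p1 or h, so these are assumptions. With p1 = 0:

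| p0 | h | B (apparent HR if true HR is 1) | Apparent HR if true HR is 0.75 | Power, as in step 1 |
|---|---|---|---|---|
| 20% | 0.90 | 1.020 | 0.765 | 0.78 |
| 40% | 0.90 | 1.042 | 0.781 | 0.71 |
| 60% | 0.90 | 1.064 | 0.798 | 0.63 |
| 20% | 0.80 | 1.042 | 0.781 | 0.71 |
| 40% | 0.80 | 1.087 | 0.815 | 0.55 |
| 60% | 0.80 | 1.136 | 0.852 | 0.37 |

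Example: p0 = 40%, h = 0.80 gives B = 1/(0.60 + 0.32) = 1.087 and 0.75 × 1.087 = 0.815. With equal prevalence, B = 1.

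**3. Allowing for timing.** The formula holds prevalence fixed and lets no case be operated on. Simulations without a pregnancy effect relax this: the hazard from step 1, surgery in 30-70% of women at a median of 2 years, and conception blocked after surgery. For a 10% lower DFS hazard the pregnancy HR was 1.02-1.04, and for 20% it was up to 1.10. The time-varying and 1:3 matched designs agreed broadly.

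**4. How large an effect of surgery do the documents support?** Section 1 gives lifetime ovarian cancer risks for healthy carriers of 45% (BRCA1) and 12% (BRCA2). Spread evenly over an assumed 30-50 years:

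- BRCA1: -ln(0.55)/50 to -ln(0.55)/30 = 0.012-0.020 per year, or 14-23% of 0.0862.
- BRCA2: -ln(0.88)/50 to -ln(0.88)/30 = 0.003-0.004 per year, or 3-5% of 0.0862.

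This assumes complete prevention. Section 1 says ovarian risk rises with age, so the share would be lower in women this young. A 10-20% reduction is thus a reasonable working range for BRCA1 and generous for BRCA2.

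**5. Do the remedies work?** In the same null simulations:

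- requiring unoperated controls at the index date gave 0.99-1.02;
- time-updated surgery status in all women gave 0.98-1.02;
- freezing surgery status at conception in pregnant women while updating it in the others gave 0.86-0.99 for effects of 10-40%.

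Freezing fails because pregnant women operated on later stay in the unoperated stratum, while non-pregnant women leave it when operated on.

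**The case against.** The strongest reply is that this is partly missing detail. The multivariate Cox models could include surgery, and surgery is to be studied as a prognostic factor. That stands as far as it goes: adjustment is not excluded. But the matching rule and the time-varying model are described specifically, and following them as written puts operated women in the comparator.

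A reader might infer more than the documents support, in three ways.

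- **That mastectomy works the same way.** It does not prevent conception, and cases may have had it before pregnancy. In null simulations of surgery that leaves conception possible, the unadjusted HR was 0.99-1.02. If cases were operated on more often (40% against 20%, h = 0.75), B = 0.90/0.95 = 0.95, in favour of pregnancy. The direction is unknown.
- **That the bias could be much larger.** Hazard reductions of 30-40% would need an effect of oophorectomy on breast events, for which the documents give no figure.
- **That the primary result will be biased against pregnancy.** Healthier women may be the ones who choose pregnancy, which acts the other way. The net direction is not established.

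Nor is inability to conceive after oophorectomy absolute, since pregnancies by assisted reproduction are included; hence hardly, rather than never.

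Two practical objections also stand. Surgery dates come only where records hold them, and the field is gynecological prophylactic surgery in general. Matching criteria are relaxed when controls run short, so another criterion could loosen existing ones.

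**Conclusion.** The concern holds for oophorectomy before the index date. The plan lets women who can hardly become cases serve as comparators on an endpoint the operation may affect, although it requests the dates needed to prevent this. The comparison may therefore be biased against pregnancy. Under assumed uptake of 30-70% and a 10-20% lower DFS hazard, the null HR is about 1.02-1.10. That is modest, but in a safety question it matters: at B = 1.087 a true HR of 0.75 would appear as 0.815, and power would fall from 0.83 to 0.55. These sizes rest on uptake, timing and effect figures that the documents do not contain. For mastectomy, the finding is only that its handling should be prespecified.

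**What to change.** **Matched analysis.** Require that a control had no bilateral oophorectomy before the index date, as an eligibility condition that is not relaxed when controls are short. Match or adjust for risk-reducing mastectomy status at the index date. State how a missing surgery date is handled.

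**Extended Cox model.** Enter oophorectomy and mastectomy as time-updated covariates for all women, pregnant and non-pregnant alike. Do not freeze status at conception, which would add falsely reassuring bias. Because this model also adjusts for surgery after pregnancy, say so when reporting it, and place it beside the model without surgery.

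**Data.** Clarify with sites which gynecological procedures were bilateral oophorectomies.

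**Cost.** SAP wording, data queries and a smaller control pool. The 1:3 set needs 3 × 200 = 600 controls. If 20%, 40% or 60% of the 2000 were excluded, 1600, 1200 or 800 would remain, though not evenly across matching strata. On the 10-year basis, comparing all remaining controls with 200 cases gives power at HR 0.75 of 0.82, 0.81 or 0.78, against the stated 0.83. The 200:600 set has 0.745 on that basis, provided all 600 controls are found.
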